Vancomycin ²		Х				Х	x	fter	ö	х	Х	X	х	X ¹	X ¹	X ¹	X ¹	X ¹	X ¹
Artificial Tears								bio		X	х	X	x	х	х	х	x	х	Х
20% Autologous Serum Drops								psy		X	X	X	X ¹	X ¹	X ¹	X ¹	X ¹	X ¹	X ¹
Symptom Assessment		X												х	x	X	X	х	X
Adverse Event Assessment		X (changes in medical status)				x	x			x	х	х	x	x	x	x	x	x	x

Cell Transplantation in the Treatment of Limbal Stem Cell Deficiency

1486 1487

1489

1504

1505 1506

1507 1508

1510

1511

1512

1513

1515

1516

1517

1488 15. PROTOCOL ADDENDUM: SECOND TRANSPLANT

1490 **15.1. OVERVIEW**

Some study participants who received CALEC and for whom epithelial defect and conjunctivalization has not resolved after 12 months may benefit from an additional transplant. Participants meeting study criteria (section 15.3) may be offered the opportunity to undergo a second procedure, either CALEC or CLAU. The following chapter outlines the protocol that will be followed for these participants. Up to three participants can receive a second transplant.

1497 **15.2. CRITERIA FOR SECOND TRANSPLANT**

- All of the following criteria must be met in order for a participant to be considered for a second transplant.
- Participant previously received CALEC (participants previously receiving CLAU will not be eligible)
- Second transplant cannot occur prior to the 12-month visit
- Presence of epithelial defect in recipient eye
 - Must have been present at 2 or more visits (>1 month between visits), any time on or after the 3-month visit
 - >1 mm in any dimension
 - (Note: Does not need to be present at the Screening/Baseline visit prior to second transplant)
- Presence of conjunctivalization / fibrovascular pannus in recipient eye
 - Must be present at the Screening/Baseline visit prior to second transplant
 - >2 mm from the limbus
 - ≥6 clock hours
 - Investigator discretion that repeat transplant has therapeutic potential
- Absence of the following in the donor eye:
 - Conjunctivalization of the cornea defined by fibrovascular pannus more than 2mm from the limbus into the cornea for ≥3 clock hours
 - Lack of limbal palisades of Vogt for ≥3 clock hours
 - History of allo-limbal transplantation
- 1518 1519

1522

1527

1532 1533

1534

1535

1520 NOTE: these criteria are independent of whether the participant meets the protocol definition of 1521 complete or partial success.

1523 15.3. INFORMED CONSENT PROCESS

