
Cell Transplantation in the Treatment of Limbal Stem Cell Deficiency

1582										
1583										
1584	15.6. STUDY PROCEDURES, MEASUREMENTS, AND VISIT SCHEDULE									
1585										
1586	For all participants choosing to undergo a second transplant (either CALEC or CLAU), the post-									
1587	operative visit and testing schedule, including all procedures, measurements and data collection, will be									
1588	the same as the current protocol (APPENDIX VI). The protocol schedule will be followed until a									
1589	common study closeout date is reached.									
1590										
1591	15.7. ANALTSIS CONSIDERATIONS 15.7.1 SΔFFTY									
1592	 Safety events of interest as defined in section 7.1.1. 									
1593	• Primary safety analysis for protocol objective: Safety events will only be tabulated up									
1595	to (not including) the date of the biopsy for the second CALEC or CLAU transplant									
1596	 Additional analysis evaluating second CALEC transplant: Safety events following the 									
1507	bionsy for the second CALEC transplant will be summarized separately									
1397	biopsy for the second CALLO transplant will be summarized separately.									
1598										
1599	15.7.2. FEASIBILITY									
1600	 Feasibility measures, as defined in section 7.1.2.: 									
1601	 Primary feasibility analysis for protocol objective: The biopsy attempts for only the 									
1602	initial CALEC transplants will be included in the primary feasibility outcome calculation of									
1603	feasibility success									
1604	 Additional analysis evaluating second CALEC transplant: The biopsy attempts for 									
1605	second CALEC transplant will be summarized separately									
1(0)										
1606										
1608	 Efficacy outcome measures as defined in section 7.2 will be evaluated the following 									
1609	ways:									
1610	 Primary efficacy analysis for protocol objective. Efficacy outcome data will only be 									
1611	included up to (not including) the date of biopsy for the second CALEC or CLAU									
1612	transplant									
1612	 Additional analyses evaluating second CALEC transplant. 									
1614	 Efficacy outcome data will be evaluated relative to original baseline through the 									
1615	latest protocol visit prior to the study closeout date									
1616	 Efficacy outcome data will be evaluated relative to second CALEC baseline 									

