 - ii. For all participants with missing data on the primary efficacy outcome at any of the time points, multiple imputation will be performed for the "Complete Success" status using logistic regression.
- 2. Primary Efficacy Analysis (CALEC versus CLAU comparison of primary efficacy outcome):
 - a. The primary efficacy outcome measure is the binary outcome "Complete Success" of the graft versus not (as defined in the Protocol). This measure will be evaluated at each of the following three time points: 3, 12 and 18 months. The number and percentage of participants meeting the "Complete Success" criteria will be tabulated at each of these time points.
 - i. Evaluate within each treatment group, in Phase B participants only. All participants who were randomized will be included regardless of whether transplant was completed. Phase B participants who discontinued prior to randomization will not be included.
 - ii. Participants who were randomized but did not receive a transplant will be included in the analysis as a failure.
 - iii. For all participants with missing data on the primary efficacy outcome at any of the time points, multiple imputation will be performed for the "Complete Success" status using logistic regression.
 - b. The two treatment groups will also be compared by computing the differences in percentages meeting "Complete Success" and 95% confidence intervals around those differences, at each time point.
 - c. As a secondary analysis, a longitudinal model of the percentage of patients with "Complete Success" at each protocol-specified examination time (including visits in-between 3, 12 and 18

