240 241 group interactions. 242 243 244 245 246 247 248 participants who completed transplant will be included. 249 ii. Missing data will not be imputed for this secondary analysis. 250 251 252 253 254 255 256 257 258 259 260 analysis as failures. 261 iii. Missing data will not be imputed for this secondary analysis. 262 263 264 265 266 267 268 269 where the data are collected. 270 271 272 continuous variable 273 274 assessment*) ≥75% 275 276 continuous variable 277 278 scale) by ≥50% 279 280 variable 281 282 7) Percentage change from baseline in OSDI score - continuous variable 283 8) Proportion of participants with decrease in OSDI score by ≥25% 284 9) Percentage change from baseline in SANDE score - continuous variable 285 10) Proportion of participants with decrease in SANDE score by ≥25% 286 * Epithelial defect surface area based on photographic images will also be evaluated. 287 288 289 290 percentages. 291 292

month) will be applied using a mixed effects logistic regression, including time by treatment

3. Secondary Efficacy Analysis (within-CALEC group evaluation of secondary efficacy outcome):

- a. The secondary efficacy outcome measure is the 3 level categorical outcome ("Complete Success", "Partial Success", "Not a Success", as defined in the Protocol). This measure will be evaluated at each of the following three time points: 3, 12 and 18 months. The number and percent of participants in each outcome category will be tabulated at each of these time points.
 - i. Evaluate in CALEC Group Phase A and Phase B participants combined. Only

4. Secondary Efficacy Analysis (CALEC versus CLAU comparison of secondary efficacy outcome):

- a. The secondary efficacy outcome measure is the 3 level categorical outcome ("Complete Success", "Partial Success", "Not a Success", as defined in the Protocol). This measure will be evaluated at each of the following three time points: 3, 12 and 18 months. The number and percent of participants in each outcome category will be tabulated at each of these time points.
 - i. Evaluate within each treatment group, in Phase B participants only. All participants who were randomized will be included regardless of whether transplant was completed. Phase B participants who discontinued prior to randomization will not be included.
 - ii. Participants who are randomized but do not receive a transplant will be included in the

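### An eye biopsied for a second transplant before month 18 has no first-graft month-18 value, and the SAP's default handling can make that exploratory success rate optimistic

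*Protocol*

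**What the plan says.** **Protocol, second-transplant addendum.** Section 15.1 offers a second CALEC or CLAU procedure to CALEC recipients "for whom epithelial defect and conjunctivalization has not resolved after 12 months", and adds: "Up to three participants can receive a second transplant". On timing, 15.2 says: "Second transplant cannot occur prior to the 12-month visit". It sets no latest date. A note in 15.2 says that "these criteria are independent of whether the participant meets the protocol definition of" complete or partial success. In 15.7.3, primary efficacy data are "included up to (not including) the date of biopsy for the second CALEC or CLAU" transplant. Further analyses of a second CALEC are listed separately there.

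**Protocol 7.2.** Complete Success is the primary efficacy outcome, assessed at months 3, 12 and 18.

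**SAP 5.0, Efficacy Analysis.** For Complete Success within the CALEC group, item 1.a.ii says: "For all participants with missing data on the primary efficacy outcome at any of the time points, multiple imputation will be performed", by logistic regression. No predictors are named. For the 3-level outcome, item 3.a.i says that only "participants who completed transplant will be included", and item 3.a.ii says: "Missing data will not be imputed for this secondary analysis". The SAP nowhere refers to a second transplant.

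**The concern.** The cut-off in 15.7.3 is sound in itself, because it stops benefit from a second graft being credited to the first. It leaves open how the first graft is scored at month 18 when the eye was re-biopsied before then.

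Neither document describes the excluded value as missing. That is an inference, but the SAP's missing-data rules are the only ones that could apply. Under them:

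- For Complete Success the value is multiply imputed. If earlier status is not in the model, the re-grafted eye receives roughly the success rate of eyes that needed no second graft.
- For the 3-level outcome the value stays blank. The SAP does not say whether the eye remains in the percentage base.

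The value is absent for a reason connected with outcome, since a second graft is offered for persistent defect and conjunctivalization. Month 18 is the latest primary efficacy time point, and Protocol 2.3 says the results will inform whether to run a Phase III trial and help size it. In a small open-label study the counting rule should be fixed before results are seen.

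**Working it through.** **The plan's own figures.** Neither document gives a precision figure for month-18 efficacy. The nearest is the SAP 4.0 table of exact binomial intervals at n = 15. It reproduces: 1/15 gives 0.2% to 31.9%, against the stated 0 to 32%. The same exact method is used below.

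**Inputs from the documents.** At most three second transplants (15.1), none before month 12 (15.2), up to 17 CALEC transplants (Protocol 5.5), and expected success of 70 to 80% (SAP 3.0).

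**Assumptions.** N = 17 eyes. k eyes are re-biopsied before month 18, and s of the other N − k succeed at month 18. For imputation on month-12 status, the re-biopsied eyes are taken to have failed at month 12. The documents do not give the real counts.

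**Formulas.**
- Non-success, kept in the base: s/17.
- Dropped from the base: s/(17 − k).
- Imputed: (s + k × p)/17, where p is the mean success probability over draws of the logistic coefficients from their estimated normal distribution.

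**Obtaining p, for k = 3 and s = 11.**
- No predictor: log(11/3) = 1.299, variance 1/11 + 1/3 = 0.424, mean p = 0.767. Rate (11 + 2.301)/17 = 78.2%.
- Month-12 status as predictor, 1 of 3 other month-12 failures successful at month 18: log(1/2) = −0.693, variance 1 + 1/2 = 1.5, mean p = 0.369. Rate (11 + 1.107)/17 = 71.2%.
- The same, with 2 of 4: p = 0.500. Rate (11 + 1.5)/17 = 73.5%.
- The same, with 0 of 3: the model separates completely. Adding pseudo-observations of total weight 2 gives p = 0.180 and 67.9%. Other ways of handling the separation gave 66.9% and 68.2%.

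**Results for month-18 Complete Success.** The three values under imputation on month-12 status correspond to none, 1 of 3 (1 of 4 when k = 1) and 2 of 4 of the other month-12 failures succeeding at month 18.

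| k | s/(17 − k) | Non-success, kept | Imputed on month-12 status | Imputed, no predictor | Dropped | Shift from non-success |
|---|---|---|---|---|---|---|
| 3 | 11/14 | 64.7% | 67.9, 71.2, 73.5% | 78.2% | 78.6% | +3.2 to +13.9 |
| 2 | 12/15 | 70.6% | 72.6, 74.9, 76.5% | 79.8% | 80.0% | +2.0 to +9.4 |
| 1 | 12/16 | 70.6% | 71.4, 72.3, 73.5% | 74.9% | 75.0% | +0.8 to +4.4 |
| 0 | – | – | – | – | – | 0 |

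**Other direction.** If j of the three re-biopsied eyes were Complete Successes when last seen, carrying that status forward gives (11 + j)/17: 64.7%, 70.6%, 76.5% or 82.4% for j = 0 to 3.

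**Sampling error.** The exact 95% interval for 11/17 is 38.3% to 85.8%, and for 12/17 about 44% to 90%. Every shift in the table lies inside these.

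**The case against.** Several points on the other side have force.

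- **A rule arguably exists.** If data excluded by 15.7.3 count as missing, SAP 1.a.ii covers them. A reader might infer that the plan has no rule at all for Complete Success, and the documents do not support that. What is unstated is the predictor set, the 3-level denominator, and whether the general rule was meant for re-grafted eyes.
- **These eyes are not shown to be failures.** That stronger reading is tempting, but 15.2 separates eligibility from success status. A defect reduced from 16 to 4 mm² has fallen by 12/16 = 75%, which is a Complete Success under Protocol 7.2, and it can still exceed 1 mm in a dimension. Section 15.2 also does not require the defect to be present at the second screening visit. Counting such eyes as non-success is therefore a choice that needs to be declared.
- **The SAP appears to be older than the addendum.** It still describes randomization to CLAU, which Protocol section 12 says v5.0 discontinued, whereas the addendum is in v6.0. Its silence is part of a wider mismatch. That explains the gap but does not close it.
- **Other analyses touch these eyes.** Protocol 7.2 examines each eye's pattern of outcomes from month 3, and 15.7.3 evaluates second-CALEC eyes against the original baseline. Neither gives a first-graft status at month 18, and the latter does not cover a second CLAU.
- **The stakes are limited.** Efficacy is exploratory, no formal test depends on it, and at most three eyes are involved. The 70 to 80% in SAP 3.0 is an expectation from literature, not a decision threshold.

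**Conclusion.** The point holds as a minor to moderate one. Protocol 15.7.3 removes the first graft's month-18 value for any eye re-biopsied between months 12 and 18. The natural reading of the SAP then imputes it without stated predictors, or leaves it blank without a stated base. Because these eyes are selected for persistent disease, both routes can make the month-18 rate optimistic.

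In the assumed three-eye case the rate moves from 64.7% to about 68 to 74% with month-12 status in the model, and to about 78% without a predictor or with the eyes dropped. The larger figure is the extreme for an outcome measured repeatedly. Only the three-eye case crosses from below 70% into the expected range; with one or two eyes every rule gives 70.6% to 80.0%. A reader might infer that the trial's efficacy conclusion turns on this rule. The documents do not support that, since every shift is within sampling error and the effect is zero if no second biopsy precedes month 18. All sizes rest on assumed counts.

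**What to change.** **Complete Success (Protocol 15.7.3 and SAP Efficacy 1.a).** Count a participant as not a Complete Success of the first graft at scheduled visits on or after the second-transplant biopsy, whether CALEC or CLAU, and keep the participant in the denominator. Limit multiple imputation to outcomes missing for other reasons.

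**Sensitivity analyses.** Report (a) multiple imputation of these values with earlier visit status as a predictor, and (b) the last pre-biopsy status carried forward.

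**3-level outcome (SAP 3.a).** Keep these eyes in the denominator and show them as re-grafted, with the last pre-biopsy category listed. Folding them into the lowest category would silently reclassify an eye that had reached Complete or Partial Success, which 15.2 allows. Also report how many eyes were re-biopsied before month 18.

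**Cost.** A few sentences in the addendum and SAP, two sensitivity rows and a listing of at most three eyes, with no new data. The SAP needs revision anyway to remove the discontinued CLAU comparison. The downside is that the month-18 rate may be lower, and an eye that was successful before re-biopsy counts as a non-success in the primary tabulation. If the sponsor prefers another rule, writing it down before the month-18 results are tabulated would also close the gap.

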- **Transplant** anticipated to occur 10 to 30 days after biopsy
- Day 1, Week 1, Week 2*, and Month 1 Visits
 - Same for Phase A and B participants
 - Only required for participants who complete a transplant
 - Visit schedule is timed from transplant date
- 832 Month 3, 6, 9*, 12, 15*, and 18 Visits
- 833 834

829

830

831

- Same for Phase A and B participants
 - Only required for participants who complete a transplant
 - Visit schedule is timed from transplant date

836

835

* The 2 week, 9 month, and 15 month visits will be optional for participants for whom travel is
prohibitive. For participants who opt out of these visits, the clinical site will work with the
participant's usual care ophthalmologist on the following:

- 840 (1) Advise that the participant follows the protocol's post-operative medication regimen, 841 although the regimen will not be enforced by the protocol in these participants.
 - (2) Request adverse events be reported to the clinical site, under a medical release from the participant.
- 844

842

843

845

846 6.8.1. STUDY SCREENING

847 Prospective participants, as defined by the inclusion/exclusion criteria, will be considered for 848 entry into this study. The study design and treatment regimen will be discussed with each 849 participant. Written informed consent will be obtained before any study-specific screening 850 evaluations are performed. The following evaluations and procedures will be performed for all 851 participants during the screening period:

852 853

857

858

861

- Informed consent process culminating in signed consent document
- Eligibility Assessment
- Record current ocular and systemic medications
- Record medical/surgical history in the past 5 years
 - Record demographic data, including date of birth, sex, and race/ethnicity
 - Review of systems
- Blood draw for testing for confirmation of eligibility criteria, including:
- 860 o Hepatitis B
 - Hepatitis C
- 862 o HIV, AIDS
 - CBC (including platelet and hemoglobin levels)

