1524 Participants meeting criteria and offered a second transplant option will undergo an informed consent 1525 process. The informed consent process will include a discussion with participants that they have the 1526 option of CLAU, CALEC, or no second transplant.

1528 15.4. SCREENING AND BASELINE

Participants consenting to undergo a second transplant, either CLAU or CALEC, will undergo the same
 screening and baseline procedures in the protocol for the initial CALEC transplant (section 6.8.1-6.8.2),
 with the following exceptions:

- The screening visit will be combined with baseline visit since the subjects receiving the second graft will have already been followed for at least a year since their initial CALEC transplant
 - The combined screening/baseline visit will include the following:

Evaluation of eligibility for a second graft

CALEC Protocol_Feb 8 2022 v6.0

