Safety and Feasibility of Cultivated Autologous Limbal Epithelial PI: [name] Cell Transplantation in the Treatment of Limbal Stem Cell Deficiency 1536 • Hematologic lab screening will include only the blood draw collected within 1-7 days as required for manufacturing of the graft per DCDI protocol 1537 Hepatitis B 1538 Hepatitis C 1539 1540 HIV 1541 Slit lamp exam 0 1542 o BCVA o IOP 1543 1544 Fundus exam or B-scan 0 • AS-OCT 1545 1546 o IVCM 1547 Slit lamp photos Symptom assessment 1548 Conjunctival swab and culture 1549 (if MRSA positive, the original protocol will be followed for vancomycin) 1550 Schirmer's test (optional) 1551 0 Punctal plus (optional) 1552 0 The visit will not require punctal plugs, bandage contact lenses, prednisolone, vancomycin, 1553 preservative-free tears and autologous 1554 serum tears as participants will already be using them as treatments from initial CALEC. The 1555 preoperative antibiotic drop will be given prior to the biopsy and transplant in the respective operative 1556 eyes, as with the initial CALEC (section 6.2.1). The Schirmer test may not be needed as participants 1557 would have had it to receive the initial CALEC and would have had plugs if necessary. . The full set of 1558 1559 labs will not be repeated as they would have been done to enter the study for the initial CALEC. The labs that are required for manufacturing of CALEC will be repeated as noted above, for participants 1560 1561 pursuing second CALEC transplant. 1562 **15.5. BIOPSY AND TRANSPLANT** 1563 1564 1565 For participants choosing to undergo CLAU The pre-operative visit will occur within 60 days after baseline and within 1-5 days prior to 1566 transplant, and testing will include slit lamp exam, visual acuity, IOP. 1567 The biopsy and transplant procedures and subsequent medication regimens will follow standard 1568 1569 care. 1570 1571 For participants choosing to undergo CALEC The post-biopsy and pre-operative visits and testing schedule, including all procedures and 1572 measurements, will be the same as the current protocol (APPENDIX VI). 1573 The CALEC manufacturing (section 6.1), biopsy and transplant procedures (section 6.2) and 1574 subsequent medication regimens (section 6.5) will follow the protocol for initial CALEC 1575 If a participant experiences failure of the biopsy to generate a viable cell sheet, the participant 1576 will not be eligible to rescreen for another biopsy attempt. The participant will be monitored by 1577 the study team for 30 days to check for any adverse events related to the biopsy procedures. If 1578 the donor eye has a complication or adverse event that does not resolve after 30 days, the study 1579 team will continue to monitor until it resolves. The participant will discontinue the study after the 1580 monitoring period. 1581

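### Primary safety and efficacy data stop at the second donor-eye biopsy, although the recipient eye carries the first graft until the second CALEC transplant

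*Protocol*

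**What the plan says.** Section 15.7.3 of the Protocol addendum limits the primary efficacy analysis to data "included up to (not including) the date of biopsy for the second CALEC or CLAU" transplant. Section 15.7.1 does the same for primary safety, counting events only up "to (not including) the date of the biopsy for the second CALEC or CLAU transplant". The next safety bullet begins "Additional analysis evaluating second CALEC transplant: Safety events following the" and goes on to put events after that biopsy in a table of their own. There is no such table for a second CLAU.

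On timing, the one listed criterion in 15.2 is "Second transplant cannot occur prior to the 12-month visit". Two other passages bear on timing but are not criteria. Section 15.1 describes candidates as those whose epithelial defect and "conjunctivalization has not resolved after 12 months may benefit from an additional transplant". Section 15.4, explaining why screening and baseline are merged, says that candidates "will have already been followed for at least a year since their initial CALEC transplant".

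Section 6.8 has a CALEC transplant "anticipated to occur 10 to 30 days after biopsy", and 15.5 applies the initial CALEC procedures to a second one. For a second CLAU, 15.5 says "The biopsy and transplant procedures and subsequent medication regimens will follow standard" care and gives no interval.

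The CALEC biopsy is taken from the donor eye (6.8.3). Primary safety events count only in the recipient eye (7.1.1). The SAP's primary safety analysis starts counting for the first graft at transplant. The SAP does not mention second transplants.

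**The concern.** The cut-off is tied to a procedure in one eye, while the primary outcomes are measured in the other. Between a second CALEC biopsy and the second graft, no surgery on the recipient eye is scheduled, and that eye is still informative about the first graft. Three consequences follow.

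- **Safety.** An infection, perforation or graft detachment in the gap is dropped from the first graft's primary rate and reported in the second-CALEC table, before that graft exists. The first graft's count starts at transplant and the second's at biopsy, so the two are handled differently. This follows from 15.7.1 alone and does not depend on the 12-month rule.
- **Efficacy.** Twelve months is a primary efficacy time point (7.2). The timing criterion restrains the transplant and the data cut is at the biopsy, so an observed 12-month assessment can fall on the excluded side. The SAP has no rule for this case other than multiple imputation of missing Complete Success status.
- **Failed second biopsy.** Under 15.5 no further biopsy is allowed and the participant leaves after the monitoring period. The wording does not say whether recipient-eye data from that period stay in the primary analysis, although no second graft was placed.

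**Working it through.** **1. Inputs.** 12-month visit at 52 weeks ± 1 week, i.e. 364 ± 7 = days 357 to 371 (6.8.11). Biopsy-to-transplant gap g = 10 to 30 days for CALEC (6.8). At most 3 second transplants (15.1). At most 17 CALEC transplants (5.5). Follow-up of 78 weeks = 546 days. Expected primary safety event rate close to 5% and expected success 70 to 80% (SAP 3.0).

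**2. The SAP's own precision figures.** Exact binomial 95% intervals reproduce: 0/15 gives 0 to 21.8% (SAP 4.0 prints 0 to 22%), and 1/15 gives 0.2 to 31.9% (printed 0 to 32%). The SAP gives no figure for the second-transplant cut-off.

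**3. When the 12-month assessment is lost, on 15.2 alone.** Let V be the visit day, T the second transplant and B = T − g the second biopsy. The assessment is excluded while the first graft is still in place when B ≤ V < T, that is, V < T ≤ V + g.
- With V = 364, it is lost if T falls by day 374 (g = 10) or by day 394 (g = 30).
- The earliest biopsy date that 15.2 permits is 357 − 30 = day 327.

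**4. The same, reading 15.1 and 15.4 as a full year before the combined screening/baseline visit.** Then B ≥ 365, and a loss needs V ≥ B. Only 12-month visits on days 365 to 371 that fall on or after the biopsy are at risk.

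**5. Safety follow-up moved out of the primary analysis.** If all three are second CALECs: 3 × 10 = 30 to 3 × 30 = 90 participant-days, out of 17 × 546 = 9,282, or 0.3 to 1.0%.

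**6. Chance of a primary event in the gap.** Assume a constant hazard h = −ln(1 − p)/546 and three second CALECs. P(any) = 1 − exp(−3hg).
- p = 5%: 0.3% (g = 10) to 0.8% (g = 30).
- p = 20%: 1.2% to 3.6%.

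**7. What one event would do.** 0/17 has an exact interval of 0 to 19.5%; 1/17 (5.9%) has 0.1 to 28.7%.

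**8. Illustration for 12-month efficacy.** Suppose 12/17 = 70.6% (44.0 to 89.7%). If three outcomes are removed and the rest analysed as complete cases, the estimate is 12/14 = 85.7% when all three were failures and 9/14 = 64.3% when all three were successes. These are outer bounds, since the SAP would impute rather than drop the outcomes.

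**The case against.** The best defence is that the second biopsy opens a new course of treatment, so a single cut at its date is simple and defensible. For donor-eye events that stands. It does not explain why first-graft data in the recipient eye should stop there.

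The second argument is that 15.1 and 15.4 show that the pathway was meant to start after a year, so a biopsy at week 48 contradicts the addendum's own premise. This has real force. A reader might infer from 15.2 and 15.7 that the plan routinely discards 12-month outcomes. The documents do not support that: they leave three sections unreconciled, and on the one-year reading the exposure shrinks to the days in step 4.

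Other tempting readings also go too far.

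- **That the lost outcomes come from the worst eyes, so success is inflated.** Section 15.2 says that eligibility is independent of complete or partial success, and the epithelial defect need not be present at the second screening.
- **That events are blamed on the second graft.** Section 15.7.1 sets a reporting window. Relatedness is decided by the Medical Monitor, whose designation is final (7.1.1, 9.2). For CLAU there is no second-graft safety table to receive an event.
- **That every re-transplanted participant loses 10 to 30 days, or that 3 of 17 twelve-month outcomes (18%) will be lost.** The interval is anticipated, and stated for CALEC only. The 18% needs all three places used and all three 12-month visits to fall in the gap.

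**Conclusion.** The point holds as a low-priority flaw in the analysis text. As written, 15.7 removes first-graft recipient-eye data collected between a second CALEC biopsy and the second transplant, and it tabulates safety events from that gap with the second graft. For a second CLAU, an event in any such gap would appear in neither 15.7.1 analysis. Loss of an observed 12-month outcome is possible, not certain, and how likely it is depends on which reading of the timing passages applies.

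The expected effect is small: at most 3 participants, at most about 1% of planned follow-up, and under a 1% chance of a displaced primary event at the SAP's expected rate. That last figure assumes three second CALECs, a 10 to 30 day gap and a constant hazard. That an excluded 12-month outcome would be imputed assumes that the SAP's missing-data rule covers it. The point is still worth correcting, because one event or outcome visibly moves an estimate in a study of this size.

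**What to change.** Change the analysis text only; no clinical rule needs to change.

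- In 15.7.1 and 15.7.3, cut recipient-eye outcomes at the second transplant, so that a 12-month assessment made before that surgery is kept.
- Cut donor-eye events at the second biopsy. State the rule for systemic events explicitly; the second biopsy date is suitable.
- Say where events after a second CLAU biopsy are reported.
- If the second biopsy fails and no second graft is placed, keep the recipient-eye data in the primary analysis until the participant leaves.
- Reconcile 15.2, 15.4 and 15.7, so that the required order of the 12-month visit, second biopsy and second transplant can be read from one place.
- Add these rules to the SAP. This is new text, since there is no second-transplant section to amend.

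The cost is a few sentences in the addendum and a short SAP paragraph. The dates needed are those of procedures that the study already performs, and no visit or measurement is added.
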